# 3.0 Outcome Measures/Endpoints

# 3.1 Primary Outcome Measures:

- 1. High resolution pressure mat: Static balance will be objectively measured using an HR Mat pressure mat (Tekscan Inc.). The center of pressure will be measured at 100Hz using the center of pressure coordinates by inbuilt software. The area of the postural sway and direction of the sway will be measured as indicators of static balance with participants standing on the pressure mat with hands at their side under 2 conditions: eyes open and eyes closed for 30 seconds each condition. A member of the research team will stand beside the participant and provide balance support as needed.
- 2. Qualisys Motion Capture system: Step length, stride length, step-width, double support period, cadence and velocity are the gait parameters that will be measured as indicators of dynamic balance using Qualisys motion capture system. The

Qualisys motion capture system will be used to assess gait as a measure of dynamic balance. The system is composed of 13-infrared cameras that capture light reflected by passive markers at a frequency of 100 Hz. It is a reliable and a valid tool for gait assessment. The biomechanical model of feet will be constructed using Visual 3D software for gait analysis. Participants will wear the same sneakers/sports shoes for each assessment. Nine markers will be placed bilaterally (18 total) at the following points: distal aspect of the great toe, 1st metatarsal, 5th metatarsal, top of the foot, medial malleolus, and lateral malleolus, proximal heel, distal heel, and lateral heel. A comfortable walking speed for each participant will be recorded using a stopwatch to measure the time it takes them to walk back and forth on a 15-meter-long-platform 3 times and the average of the 3 trials will be calculated. Participants will then walk at the same speed at least 5 times or until the entire gait cycle is captured by the infrared camera system twice. Gait cycle is defined as heel-strike to heel strike on the dominant foot. A couple of practice trials will be performed to ensure understanding of the procedure and verbal prompting will be used to remind the participant to walk typically. Biomechanical models of feet will be constructed using Visual 3D software for gait analysis. If the participant is unable to perform this assessment as described, it will be rescheduled up to two times before study dismissal.

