# 7.0 Study Procedures

1. Prior to day 1: Informed consent materials, a screening questionnaire, and Autism Spectrum Screening Questionnaire (ASSQ) will be sent electronically to parents/caregivers. Participants and parents/caregivers in both groups will be given access to a video of the data collection space, intervention space setting, and a short introduction of the research personnel for review. If the participants are 18 years or older, this information will be shared with the participants directly and they will fill the questionnaires. If the participant is less than 18 years old, the information will be shared with the parent/legal guardian to be completed. Additionally, The ASSQ is a commonly used valid and reliable 27-item checklist to be filled in by parent/caregiver for assessing symptom characteristics of ASD. The ASSQ can be completed in 10 minutes using a 3-point Likert scale with possible score range being 0 of 54 with 19 being a cut off for a parent/caregiver rating identifying ASD. This tool will be used as a part of demographic screening of the participants prior to the pre-intervention day and used to better describe individual autism symptoms than is available in a medical or educational diagnosis. The researcher will subsequently contact participants and parent/caregiver to review the information, check for understanding, (particularly the terminology used in the ASSQ), assess eligibility via screening tool and address any other questions prior to study inclusion and visit.

Study participation will require 9 visits: 1 pre-intervention visit, 6 intervention visits, 1 post-intervention visits and 1 retention visit. Participants will receive \$10 Amazon or Kroger gift card after completing each session with total possible compensation of \$90.

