# 2. Pre-intervention/session 1:

2.1 As part of familiarization, participants will be shown and allowed to handle the different data collection instruments and ask questions. The intervention group will be shown the Nintendo Switch to get familiarized with their operation and functions. Parents/caregivers of the participants (under 18 years of age) in the intervention group will be handed over the Nintendo Switch Sports

to be connected at their home for the duration of intervention. Participants 18 years of age or older will be given the device. Researchers will provide any technological assistance required for this purpose.

2.2 Weight will be recorded using a calibrated scale and height measured using a stadiometer. The Edinburgh Handedness Inventory-short form (EHI-SF) will be used to assess hand-preference. It is a valid and reliable 4-item checklist of everyday tasks and participants score their hand preference on 5-point Likert scale (for each item, always right= 100, usually right= 50, usually left= 50, always left= -100). A researcher will read the rating scale to those with low literacy level. Handedness will be determined using a laterality quotient. The laterality quotient is interpreted as left handers (-100 to -61), mixed handers (-60 to +60) and right handers (61 to 100). Hand length will be calculated using a tape cloth, measured from greater tuberosity to distal end of middle digit on the right hand and leg length iliac crest to ground on the right leg.

Participants will be shown the different data collection instruments to handle, get familiarized and ask questions. Participant's hand dominance will be recorded using the Edinberg Handedness Inventory-short form. Participant's foot dominance will be recorded by asking them to kick an imaginary ball placed on the ground in front of them. Practice trials for balance and gait assessments will be conducted to ensure understanding of the protocol. Baseline assessments for posture and gait will be performed.

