## 4. Post-intervention/session 8 and 9:

Static and dynamic balance will be reassessed as previously described to examine retention effects of the VR active gaming intervention (see study calendar). Session 8 will be at least 3-5 days after session 7. Parent/caregiver will return the Nintendo Switch Sports to the researcher. Session 9 will be 4 weeks after session 7. Each session will be for approximately 60 minutes.

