# 10.0 Study Withdrawal/Discontinuation

After reviewing the consent and/or assent form and having their questions answered, participants may decide to sign the forms and participate in the study. Or they may choose not to participate in the study. The decision is up to the participants. If they choose not to participate in this study or change their mind after signing the consent document, it will not affect their usual medical care or treatment or relationship with Indiana University.

If participants change their mind and decide to leave the study in the future, the study team will help them withdraw from the study safely. If they decide to withdraw, they should contact one of the a researchers to make them aware. Researchers will instruct the participant to stop playing the Nintendo Switch Sports and the researcher will collect the gaming console from the participant.

The researchers may stop the participation in the study even if participant do not want to stop if there is any incidence which leads to participant acquiring any exclusion criteria of this study such as any neurological or orthopedic condition affecting balance, epilepsy, or any type of injury that prevents you from continuing your participation during the data collection process of the study.

The PI will be responsible for data and safety monitoring. The study team will meet at least biweekly to discuss any difficulties while conducting the experimental protocols and review the data. [name] will always be available online when data collection is occurring. Minutes of each of the meetings will be maintained on the designated One-Drive folder for the Physical Activity Research lab.

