# 11.0 Statistical Considerations

According to prior research study examining the similar paradigm using Xbox games (Ghobadi et al. 2019), we predict the medium effect size (f=0.25) to detect significant changes within groups, between groups and effect of timepoint on static and dynamic balance. Power analysis

(using G\*power 3.1.9.7 software) indicates 14 subjects in each group to have 0.8 power to detect this effect (alpha 0.05). To account for the likelihood of attrition and noncompliance, total 40 participants are being recruited. Data from participants who engage in all the intervention sessions will be included in the analysis.

SPSS (Statistical Package for the Social Sciences) and MATLAB will be used for processing and analyzing the data. Participants demographic and health characteristics will be compared using paired sample t-tests. Intention to treat analysis will be used for addressing effects of treatment or control on static and dynamic balance. The dependent variables for static balance include: 1) sway area of 95% confidence ellipse for center of pressure(mm²), 2) direction of center of pressure sway as anteroposterior and mediolateral (mm). The dependent variables for dynamic balance are: 1) step length (m), 2) stride length (m), 3) step width (m), 4) double support period (sec), 5) cadence (steps/min) and 6) gait velocity (meters/min). Total PBS score will be dependent variable for both static and dynamic balance.

Two-way repeated measures ANOVA (analysis of variance) will be used to determine 1) within intervention and control group, for assessing the main effect of group, 2) between intervention and control group for assessing main effect of time, and 3) between - within interaction for assessing the interaction term. Statistical significance will be declared if  $p \le 0.05$  (two-tailed).

[name] ([contact]) will assist with the statistical considerations.

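### A failed gait capture leads to dismissal from the whole study, which stops PBS and sway collection in participants who appear already allocated

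*Combined protocol and SAP*

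**What the plan says.** **The rule.** Section 3.1, item 2 (Qualisys motion capture): "If the participant is unable to perform this assessment as described, it will be rescheduled up to two times before study dismissal". It allows three attempts in all. It names no visit and is silent on the other two instruments and on data already collected.

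**The visits.** Section 7.0 plans "1 pre-intervention visit, 6 intervention visits, 1 post-intervention visits and 1 retention visit". Gait, sway and PBS are measured at sessions 1, 8 and 9. For the last two, Section 7.0 item 4 says: "Static and dynamic balance will be reassessed as previously described to examine retention effects of the VR active gaming intervention".

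**Timing of allocation.** Before day 1, Section 7.0 already speaks of two groups: "Participants and parents/caregivers in both groups will be given access to a video of the data collection space". At session 1, the baseline visit, "The intervention group will be shown the Nintendo Switch to get familiarized with their operation and functions" and "Parents/caregivers of the participants (under 18 years of age) in the intervention group will be handed over the Nintendo Switch Sports".

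**Other removal rules.** Section 10.0 lets researchers stop participation "if there is any incidence which leads to participant acquiring any exclusion criteria of this study", with injury among the examples. Gait-capture failure is not mentioned there, and Section 4 has no gait-capture criterion.

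**Analysis.** Section 11.0: "Intention to treat analysis will be used for addressing effects of treatment or control on static and dynamic balance". The same section also limits the analysis to participants who took part in every intervention session. The model is a two-way repeated measures ANOVA, with no missing-data method. Section 3.2 names PBS total score as the primary endpoint.

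**The concern.** PBS and the pressure mat can be done without markers or cameras. A participant who cannot complete the motion-capture walk may still give valid results on both. As written, the rule ends that person's participation, so the primary endpoint is lost because a different instrument failed.

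The trigger is an outcome measurement, and it appears to act after allocation. Gait is the trial's own measure of dynamic balance, so removal may depend on ability in the domain under study. If removals differ between arms, the arms compared are no longer those that were allocated. An intention-to-treat analysis then lacks the follow-up it needs, and Section 11.0 does not say how to handle the gap.

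**Working it through.** **1. What is lost, by visit of failure**

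| Third failed attempt at | PBS and sway visits no longer collected | Status under Section 11.0 |
|---|---|---|
| Session 1 | Sessions 8 and 9 (all follow-up) | Intention to treat would count the participant; the all-sessions sentence excludes them, because the protocol stopped them |
| Session 8 (if the rule applies there) | Session 9 | Meets the all-sessions condition; earlier data drop out only if the ANOVA uses complete cases |
| Session 9 (if the rule applies there) | No later visit | Both statements keep the PBS and sway data |

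**2. Reproducing the planned sample size**

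Inputs from Section 11.0: f = 0.25, alpha 0.05, power 0.8, 14 per group, 40 recruited. Assumed because not stated: three time points (m = 3), correlation rho = 0.5, sphericity.

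For the group-by-time interaction, lambda = f² × N × m / (1 − rho) = 0.0625 × 28 × 3 / 0.5 = 10.5, with 2 and 52 degrees of freedom. Power is 0.812, so 14 per group reproduces. A between-group main effect at the same f would need N = 86, so the plan's figure is not sized on that effect.

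**3. Effect on power**

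40 − 28 = 12 losses are affordable (12/40 = 30%). They must cover attrition, noncompliance and gait dismissals together.

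| Dismissed | No other attrition | With 20% other attrition |
|---|---|---|
| 0% | n = 40, 0.935 | n = 32, 0.866 |
| 10% | n = 36, 0.906 | n = 28, 0.812 |
| 20% | n = 32, 0.866 | n = 25, 0.760 |
| 30% | n = 28, 0.812 | not calculated |

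If a failed capture cost only the gait variables, PBS and sway would keep the 0% row.

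**4. Effect on the comparison (illustration only)**

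The documents give no failure rate, overall or by arm. Assume that the lowest fraction p on gait ability is dismissed, that gait ability is normal, and that it correlates r with the outcome. The shift in that arm's mean is r × φ(z_p) / (1 − p), in SD.

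- p = 0.10: 0.1755 / 0.90 = 0.195; times 0.5 gives 0.097.
- p = 0.20: 0.2800 / 0.80 = 0.350; times 0.5 gives 0.175.

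| Dismissed, arm A vs arm B | Shift in difference, r = 0.2 | Shift in difference, r = 0.5 |
|---|---|---|
| 10% vs 10% | 0 | 0 |
| 10% vs 20% | 0.03 SD | 0.08 SD |
| 0% vs 20% | 0.07 SD | 0.18 SD |

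**5. Scale for comparison**

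Let D be the final between-arm difference in change. If the arm differences at the three visits are 0, D, D, then f = D/√18 and D = 0.25 × 4.243 = 1.06 SD. If they are 0, D/2, D, then f = D/√24 and D = 0.25 × 4.899 = 1.22 SD. The shifts in step 4 are small against these planned effects.

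**The case against.** The strongest defence is that the sentence is a baseline feasibility check. Section 7.0 item 2.3 repeats the gait procedure almost in full and leaves the dismissal sentence out, and item 4 describes how balance is reassessed without restating dismissal. Gait is the whole of Specific Aim 2, so there is a reason to require it. Section 4 requires the ability to follow instructions and excludes conditions that limit mobility. With familiarization, practice trials and three attempts, failures may be few. Power tolerates 12 losses.

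Much of this stands. Application at sessions 8 and 9 is a natural reading but an inferred one. The baseline reading does not rescue the rule, though, because arms appear to be known by session 1. That timing is itself well supported rather than stated outright.

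A reader might infer more than the documents support:

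- **That PBS and sway data are deleted.** No section says collected data are discarded, and a session 9 failure loses no later visit.
- **That the bias reaches 39% or 55% of the target effect.** Removing the lowest 10% or 15% of one arm does raise its mean by 0.195 or 0.274 SD, and 0.195/0.5 and 0.274/0.5 give those percentages. But this assumes perfect selection on the outcome and no dismissals in the other arm. It also uses d = 0.5, whereas the plan's figure reproduces as an interaction with a target of 1.06 to 1.22 SD. If selection acts on baseline level with rho = 0.5, later means move half as far, so the change score shifts in the opposite direction.
- **That those removed are the participants with the poorest balance.** This is plausible, but nothing in the documents shows it.
- **That Sections 3.1 and 10.0 flatly contradict each other.** Section 10.0 is permissive and does not claim to be exhaustive.
- **That rescheduling must break the 3–5 day window for session 8.** It can, but three attempts on days 3, 4 and 5 would fit.

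**Conclusion.** The concern holds in a limited form. Followed as written, the rule stops collection of the primary endpoint and of sway in participants who appear to be allocated already, because an unrelated instrument failed. That is avoidable, and it conflicts with the promised intention-to-treat analysis.

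The main risk is selection rather than power. The comparison is biased only if dismissal differs between arms in rate or in kind; equal selection in both arms mainly limits generalisability. At r = 0.5 the illustrative shift is 0.08 to 0.18 SD, and its direction cannot be told from the documents. These sizes rest on an assumed correlation and assumed failure rates.

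This should be fixed. Confidence is medium on whether the rule reaches sessions 8 and 9.

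**What to change.** In Section 3.1, item 2, replace the dismissal consequence with wording such as: *If the gait capture cannot be completed after two further attempts, the gait variables for that session are recorded as missing, with the reason. The participant remains in the study. PBS and pressure-mat assessments continue at that session and at all later planned visits, and are analysed as allocated.*

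Then:

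- Report gait-capture failures by arm and visit.
- State a missing-data method in Section 11.0, for example a mixed model that uses all available visits.
- Reconcile Section 3.1 with Section 10.0, and reconcile the two analysis-set statements in Section 11.0. Otherwise analysis as allocated will still clash with the all-sessions restriction.
- If gait capability is meant as an entry requirement, list it in Section 4 and check it before allocation.

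The cost is a short text change and some missing gait values. No visits are added beyond those planned.

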# 3.2 End points:

- 1. Primary endpoints: Reduction in PBS total score by 3.7 points. This is in accordance with the MCID range reported by Chen et al, 2013 as 3.66-5.83 for PBS in children with neuromotor impairments.
- 2. For static balance: 1) reduction in the sway area of 95% confidence ellipse for center of pressure, 2) reduction in mediolateral direction of the postural sway.
- 3. For dynamic balance: Reduction in 1) step width, 2) double support period. Increase in 1) step length, 2) Cadence, 3) Gait velocity
- 4. Secondary endpoints: Safety.

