3. Pediatric Balance Scale (PBS): The PBS will be used to assess static and dynamic balance. It is a valid and reliable clinical balance assessment tool for children and youth with motor impairments. It is a 14-component battery that evaluates daily living tasks such as sitting to standing, transferring from one chair to another, and sitting and standing without support. Item numbers 1-3 and 9-14 are specific to dynamic balance while item numbers 4-8 are specific to the static balance. Participants are graded as 0-4 on each component of the scale with 56 being the highest total score achieved. A higher score indicates better postural control. Interpretation of the scores is as follows: 41 to 56 denotes a low fall risk, 21 to 40 a medium fall risk, and 0 to 20 a high fall risk. The PBS takes fifteen to twenty minutes to administer. A different researcher from the study team will record the PBS to

avoid any assessment bias. The researcher will demonstrate each task and the participant will be allowed 1-2 practice trials before official assessment as per the instructions provided in the tool. The researcher is well trained in administrating the PBS. Inter- and Intra-rater reliability will be checked at least four times throughout the course of the study by scoring a videotaped administration of the tool. An intraclass correlation of 0.9 must be achieved to avoid retraining on the PBS.

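### Section 3.2 makes a 3.7-point PBS change the primary endpoint, but Section 11 never uses that criterion, and its level, visit, comparator and direction are not settled

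*Combined protocol and SAP*

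**What the plan says.** Section 3.2 (End points) opens with "Primary endpoints: Reduction in PBS total score by 3.7 points". It supports the size with an MCID range of 3.66 to 5.83 from a cited study in children with neuromotor impairments. It names no visit and no comparison with control, and does not say whether the figure is per participant or a mean.

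Section 3.1 lists three primary outcome measures: the pressure mat, motion capture and the PBS. It describes the PBS as a 14-item scale, each item scored 0 to 4, with a maximum of 56, and states that "A higher score indicates better postural control".

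Section 11.0 (Statistical Considerations) says "Total PBS score will be dependent variable for both static and dynamic balance", alongside three sway variables and six gait variables. For the model, "Two-way repeated measures ANOVA (analysis of variance) will be used to determine" effects of group, time and their interaction. The only decision rule is "Statistical significance will be declared if" p ≤ 0.05, two-tailed. The sample size rests on a standardised effect: "we predict the medium effect size (f=0.25) to detect significant changes within groups, between groups and effect of timepoint", giving 14 per group, with 40 recruited to allow for losses.

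Section 2.1 frames both aims as VR gaming versus traditional balance exercises. Section 7.0 gives the control arm supervised balance training, with reassessment at session 8 (at least 3–5 days after the last intervention session) and session 9 (4 weeks after it).

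**The concern.** A primary endpoint stated as a change of a given size needs an analysis that uses that size. Here the criterion stands in Section 3.2 and the analysis in Section 11, and nothing joins them. Two analysts following the plan could report different primary results: the share of participants gaining 3.7 points, the mean gain in the VR arm, or the difference between arms, each at session 8 or session 9. The choice could then be made after the data are seen.

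The control is active. If both arms improve by a similar amount, the time effect can be significant and both arms can gain 3.7 points, yet neither result shows an advantage of VR, which is what Section 2.1 asks. A significant between-arm difference could also be smaller than the plan's own relevance threshold, with no stated rule for describing it.

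**Working it through.** **1. Side-by-side reading.** The figure 3.7 and the MCID appear only in Section 3.2. Section 11 has no responder definition, no confidence interval, no comparison with 3.7 and no named primary effect or visit. Its dependent variables number 1 (sway area) + 2 (sway directions) + 6 (gait) + 1 (PBS total) = 10. On direction, Section 3.2 says reduction and Section 3.1 says higher is better. Read literally, the endpoint would be met by worsening.

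**2. The plan's own sample size.** Inputs from Section 11: f = 0.25, alpha 0.05, power 0.8. Three assessments (sessions 1, 8, 9) come from Section 7.0. Assumed, because not stated: correlation 0.5 between visits and sphericity. For the interaction or time effect, λ = f² × N × m / (1 − ρ) = 0.0625 × 28 × 3 / 0.5 = 10.5 on 2 and 52 degrees of freedom. Power is 0.812, so 14 per group reproduces. Planned recruitment of 40 allows for 1 − 28/40 = 30% loss.

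This does not bring in 3.7. For a difference in change held at both follow-up visits, f = 0.25 corresponds to 1.06 SD. That equals 3.7 points only if the PBS SD is about 3.7 / 1.06 ≈ 3.5, which the documents do not say.

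**3. How far significance can sit from 3.7.** The documents give no SD of PBS change, so a range is assumed. A two-sample t test on change to one visit stands in for the three-visit ANOVA. Smallest significant difference = t(0.975, 2n − 2) × SD × √(2/n):

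- n = 20 per arm: 0.640 × SD
- n = 14 per arm: 0.777 × SD

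| Assumed SD of change | Smallest significant difference, 20 per arm | Same, 14 per arm | Power for a 3.7-point difference, 20 per arm | Same, 14 per arm |
|---|---|---|---|---|
| 2 | 1.28 | 1.55 | >99% | >99% |
| 3 | 1.92 | 2.33 | 97% | 88% |
| 4 | 2.56 | 3.11 | 81% | 65% |
| 5 | 3.20 | 3.88 | 63% | 47% |
| 6 | 3.84 | 4.66 | 48% | 35% |

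The significance threshold passes 3.7 points at SD = 3.7 / 0.640 ≈ 5.8 with 20 per arm and 3.7 / 0.777 ≈ 4.8 with 14 per arm.

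**4. The shared time effect.** A pre–post change pooled over 40 participants is significant at t(0.975, 38) / √40 × SD = 0.32 × SD, or 0.96 points at an SD of 3. This needs no difference between arms.

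**The case against.** The endpoint variable is analysed. Total PBS is a named dependent variable, the model includes the group-by-time interaction, and mean change by arm is an ordinary output that a reader could set against 3.7. Section 2.1 makes the intended comparison with control recoverable. Any test of zero difference can be significant below an MCID, so that feature is not peculiar to this plan. All the point values depend on an SD that the documents do not give.

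Most of this stands. A reader might infer that the primary endpoint is analysed nowhere, that the p-value is unrelated to it, that it will never be reported, or that the trial can claim success without it. The documents do not support those readings: PBS total is tested, Section 11 defines statistical significance but no rule for success, and nothing says that changes in PBS will go unreported.

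The objection does not remove the gap itself. That a comparison can be recovered from the aims does not make it the pre-specified primary one. Section 11 lists three effects without ranking them, and neither section fixes the level or the visit for 3.7. The contradiction in direction remains as well.

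**Conclusion.** The concern holds as a mismatch between the declared endpoint and the declared analysis. The 3.7-point criterion is undefined in level, visit and comparator, is worded in the wrong direction for the scale, and is not used in Section 11. None of this depends on any assumed SD.

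The numerical part is an illustration only. Under the t-test stand-in, a significant arm difference can fall short of 3.7 points unless the SD of change exceeds about 5.8 (20 per arm) or 4.8 (14 per arm). It does not show that a result below 3.7 is likely, nor that the trial would be presented as successful on one. The matter should be settled before outcome data are examined, because a choice made afterwards would not be credible.

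**What to change.** In Section 3.2:

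- Correct the direction to an increase.
- State where the PBS ranks among the three primary outcome measures of Section 3.1.
- Name one primary visit. Session 8 is a reasonable choice, with session 9 as retention; the sponsor may prefer otherwise, since Section 1.0 makes 4-week retention a stated purpose.
- Define the endpoint as the between-arm difference in PBS total at that visit.

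In Section 11:

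- Make the baseline-adjusted between-arm mean difference with 95% CI the primary PBS analysis.
- State that p ≤ 0.05 shows only a difference from zero, and that the estimate and CI will be reported beside 3.7.
- Fix in advance the rule for calling the difference clinically relevant, for example a point estimate of at least 3.7. The rule must be explicit: requiring the lower confidence limit to reach 3.7 would need an observed difference of about 3.7 + 1.9 = 5.6 points at an SD of 3 with 20 per arm, which is much stricter.
- Report as supportive only the number per arm improving by at least 4 points (totals are whole numbers). Note the ceiling: anyone starting at 53 or above cannot gain 4 on a scale that ends at 56. Baseline PBS is not given, so this table may prove uninformative.
- Say that the sample size rests on f = 0.25 and not on 3.7 points, and show the power for 3.7 over a range of SDs. At an assumed SD of change of 4 it is about 65% with 14 per arm and 81% with 20.

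The cost is wording in two sections and one table, with no new visits or measurements. A significant difference below 3.7 could no longer be called clinically relevant, and the power statement may show that the trial is small for a difference of that size.
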